6.6 Randomization Plan

Eligible participants will be randomized in a 1:1 ratio to the TAU+SCT and TAU arms. The randomization process will be performed by computer at a centralized location. Randomization will be stratified by site and by whether a stimulant-positive UDS result was obtained during baseline/ screening (yes/no). The block size chosen will be adequate to ensure approximate treatment balance. The number in each treatment group will never differ by more than a factor of KB/2 where B is the block size and K is the number of strata.

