7.4 Active Treatment Phase

The active treatment phase is 10 weeks in duration. During this time, participants in both treatment conditions will participate in the substance-abuse treatment typically offered by the CTP. Participants randomized to the TAU+SCT arm will receive individual smoking-cessation counseling consisting of approximately one ten-minute counseling session per week during study weeks 1 through 10. In addition, all TAU+SCT participants will receive bupropion XL (300 mg/day) and, during the post-quit treatment phase, the nicotine inhaler (6-16 cartridges per day ad libitum). Finally, all TAU+SCT participants will receive contingency management in which drawings for prizes are given for smoking abstinence as assessed by carbon monoxide (CO) levels during the post-quit phase of the trial (i.e., weeks 4-10). The TAU+SCT participants will have a target quit smoking day at the end of study week 3. Following the final week 10 visit, TAU+SCT participants will be provided with a 3-day bupropion XL dose taper, in which 150 mg is taken once per day and with a 3 week nicotine inhaler taper. Participants in both conditions will meet with study staff twice weekly to complete study assessments as outlined in Table 2, with the constraint that visits ideally occur on nonconsecutive days.

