11.3.1 Primary Outcome

The primary hypothesis is that a significantly greater percentage of TAU+SCT, relative to TAU, participants will be stimulant-free during the weeks of the active treatment phase. For each participant, a stimulant-free week is defined as a week in which both urine samples test negative for stimulants and the participant self-reports no illicit stimulant use. A stimulant-positive week is defined as a week in which at least one urine sample tests positive for a stimulant or during which the participant self-reports illicit stimulant use. However, in the analysis of data from any clinical trial, strategies must be employed for handling missing data. In this trial, data for a week in which both urine samples are missing and the participant self-reports no illicit stimulant use will be treated as missing. For a week in which one stimulant-free UDS is produced, the second urine sample is missing, and the participant self-reports no illicit stimulant use or the self-report data are missing will be treated as negative (Table 6).

Data will be analyzed using a generalized linear mixed model (GLMM) for repeated-measures analysis (Brown and Prescott, 1999). Suppose Y represents the vector of observed response data, X and Z the fixed and random effects design matrices, and α and β be the vectors of fixed and random effects, respectively. Then, the GLMM model formulation assumes that

$$\mathrm{E}(\mathrm{Y}|\beta) = g^{-1}(\mathrm{X}\alpha + \mathrm{Z}\beta),$$

where $E(Y|\beta)$ is the expected value of Y conditional on the random effects vector, g^{-1} is the inverse link function, and $X\alpha + Z\beta$ is the linear predictor. The response variable Y will be modeled using the logit link function, i.e., $g(\mu) = \log(\mu / (1 - \mu))$. Fixed effects will include treatment group and week, while random effects will include site. SAS Proc GLIMMIX will be used to fit the model as follows:

proc glimmix; class site treatment; model Y = treatment week treatment*week / dist=binary link=logit covb solution; random intercept / subject=site; random _*residual_*/subject=patientid type=cs; run;

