11.4 Sample Size Estimate

The minimum sample size required to achieve 80% power using an alpha level of 0.05 (two-sided) and a 1:1 randomization ratio was computed based on a repeated measures study design that takes into account that the data are binary and can be correlated across repeated measurements (Rochon, 1998). We assumed a compound symmetry covariance structure to be conservative (correlation between 2 successive time points does not change over time), as well as a maximum correlation between any 2 time points of 0.65. The higher the assumed correlation between time points, referred to as phi, the less information that we gain from successive measurements, thus requiring a larger sample size. The assumption of 0.65 for the present study is based on the phi calculated for the stimulant UDS results from the subgroup of cocaine dependent participants in CTN-0009, a study that evaluated the impact of concurrently providing smoking-cessation treatment with substance-abuse treatment.

The probability of stimulant-free urines in the TAU group is another key assumption in determining sample size. A review of the stimulant UDS results for cocaine-dependent participants from three prior CTN studies, CTN-0009, CTN-0015 (Seeking Safety for women with PTSD and substance-use disorders), and CTN-0006 (Contingency management for stimulant abusers) produced probabilities ranging from 0.55 to 0.75, with the lower probabilities (i.e., 0.55) requiring larger sample sizes. Based on these prior studies, we assumed a probability of 0.6 for stimulant-free urines in the TAU group. A final key consideration in calculating sample size is the size of the group difference to be detected. The present study has been powered to detect the lower limit of a clinically meaningful effect. Specifically, this study will detect a group difference if the probability of stimulant-free urines in the TAU+SCT group is at least 0.7.

The sample size yielded from the assumptions outlined above is 528, with 264 in each treatment group. As described in section 11.6, an interim analysis to evaluate the accuracy of the assumptions made in calculating this sample size will be conducted, with an adjustment made to the sample size if needed.

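### The primary model omits the baseline stimulant-UDS stratum used for randomization, so the test of the overall treatment effect is conservative if that stratum is prognostic

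*Protocol*

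**What the plan says.** Protocol section 6.6 sets two stratification factors: "Randomization will be stratified by site and by whether a stimulant-positive UDS result was obtained during baseline/ screening (yes/no"). The synopsis (section 3.0) names the same two.

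Section 11.3.1 specifies the primary analysis down to SAS code. In words: "Fixed effects will include treatment group and week, while random effects will include site". In code: "model Y = treatment week treatment*week / dist=binary link=logit covb solution", with a random intercept for site and a compound-symmetry residual structure within participant. Baseline UDS appears in neither. The section explains why site is adjusted for and does not mention the second factor.

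Sections 11.3.1 and 11.3.4 leave one route for other covariates: a variable associated with attrition at the 0.10 level is added to later analyses that rely on data missing at random.

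On the tested quantity, section 11.1.1 and the opening of section 11.3.1 state the primary hypothesis as a higher percentage stimulant-free in the TAU+SCT arm over the weeks of active treatment. Section 11.4 sizes the trial on the same quantity: "we assumed a probability of 0.6 for stimulant-free urines in the TAU group", to be detected if "the probability of stimulant-free urines in the TAU+SCT group is at least 0.7". Later in section 11.3.1, however, the intervention effect on change from baseline is assigned to the treatment-by-week interaction.

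**The concern.** Stratified randomization balances the arms on baseline UDS, so the true sampling variation of an overall treatment comparison shrinks if that factor predicts outcome. A model that leaves the factor out does not register the shrinkage: the between-stratum variance stays in the error, and the model-based standard error describes a less balanced trial than the one that was run. The test then rejects less often than 5% under the null and has less power than an adjusted analysis of the same data.

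There is also a question of prespecification. Whether baseline UDS is in the primary model would depend on an attrition test in the trial's own data, although the factor is known at randomization. Including it from the start would also support the missing-at-random assumption on which the mixed model relies.

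**Working it through.** **Inputs from the protocol.** Section 11.4: "The minimum sample size required to achieve 80% power using an alpha level of 0.05 (two-sided) and a 1:1 randomization ratio was computed"; 0.6 versus 0.7; compound symmetry with a "maximum correlation between any 2 time points of 0.65"; 264 per arm, 528 in total. Section 7.4: "The active treatment phase is 10 weeks in duration". Section 11.4 does not state the number of repeated measures; ten weekly outcomes are assumed here.

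**Step 1: the plan's own figure.** The design effect for a mean of m equally correlated measures is (1 + (m − 1) × 0.65)/m. For m = 10 it is (1 + 5.85)/10 = 0.685. A single-occasion comparison of 0.6 with 0.7 needs 356 per arm (pooled) or 376 with continuity correction.
- 376 × 0.685 = 257.6, so 258 per arm and 516 in total, about 2% below 528.
- 356 × 0.685 = 243.9, so 244 per arm and 488 in total, about 8% below.

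The stated 528 is therefore approximately reproduced. No stratum term is among its stated assumptions.

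**Step 2: standard error and power for the overall effect at 264 per arm, ignoring strata (logit scale).**
- Log odds ratio: ln(0.7/0.3) − ln(0.6/0.4) = 0.442.
- SE under 0.6 versus 0.7: √[(0.685/264) × (1/0.24 + 1/0.21)] = 0.152.
- SE under the null at 0.6: √[(0.685/264) × (2/0.24)] = 0.147.
- Power: Φ(0.442/0.152 − 1.96) ≈ 0.83.

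**Step 3: effect of the omitted stratum, by simulation.** The settings were 1,000 trials each, N = 528, ten weeks, overall within-participant correlation 0.65, complete data and no site effect. Randomization was balanced within the UDS stratum. A marginal logistic model with exchangeable correlation and model-based SEs was fitted with and without the stratum. The protocol gives no prevalence or association, so 30% or 50% baseline-positive and stratum odds ratios (OR) of 3, 6 and 12 are assumptions. Ranges run over the two prevalences.

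| Overall effect | OR 3 | OR 6 | OR 12 |
|---|---|---|---|
| Mean model SE, null, no stratum term | 0.147 | 0.147 | 0.147 |
| True sampling SD | 0.139-0.144 | 0.125-0.126 | 0.110-0.112 |
| Model SE too wide by (ratio of the two) | 2-6% | 17-18% | 31-34% |
| Type I error, no stratum term | 4.6-4.9% | about 2.5% | 0.7-1.0% |
| Type I error, with stratum term | 5.5-6.1% | 4.0-4.9% | 4.6-5.0% |
| Power, no stratum term | 85% | 85-87% | 88% |
| Power, with stratum term | 86-88% | 90-91% | 96-97% |
| Power forgone (points) | about 2 | 4-6 | 7-8 |

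The Monte Carlo standard error of a 5% rate is √(0.05 × 0.95/1000) = 0.7 points, so the type I error at OR 3 cannot be told apart from 5%. With a stratum odds ratio of about 1, power is 83% with or without the term.

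**Step 4: treatment-by-week slope, same simulation.** Without the stratum term, the model SE (about 0.012) matches the sampling SD to within 0.001, type I error is 4.0-5.6%, and power is about 92-93%. With the term, power is 91-94%, the same within simulation error. The slope is a within-participant contrast, so a factor constant over time does not add to its error.

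**Step 5: percentage scale, closed form and simulation.** Assume 50% baseline-positive and a gap d between strata in the probability of a stimulant-free week. The participant-mean variance is 0.24 × 0.685 = 0.1644, and the share due to the stratum is f = 0.25d²/0.1644. For d = 20, 35 and 50 points, f = 6%, 19% and 38%. Type I error without adjustment is 2Φ(−1.96/√(1 − f)) = 4.3%, 3.0% and 1.3%. In a separate simulation of the standardized difference (N = 528), the SE falls from 3.42 points to 3.31, 3.06 and 2.63 with adjustment. Unadjusted type I error is 4.9%, 2.8% and 1.6%. Power rises from 84%, 86% and 89% to 85%, 90% and 97%.

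**The case against.** The strongest objection is that the protocol assigns the intervention effect to the treatment-by-week interaction, and for that parameter the omission costs nothing (step 4). This stands, and it limits the consequence to the overall effect. It does not remove the point: the hypothesis and the sample size are both about the overall percentage, and a slope alone does not test that.

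A reader might infer that the trial is underpowered, or that the benefit of stratifying is lost altogether. The documents do not support either. The 80% in section 11.4 does not assume a stratum adjustment, and the unadjusted test still has about 83-88% power at 528 with complete data. Unadjusted power rises with the strength of the stratum, so part of the benefit survives through balance. The error is also on the conservative side; false positives are not inflated.

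A reader might also expect adjustment to narrow the standard error in the specified logit model. It does not: under 0.6 versus 0.7 the SE goes from 0.152 to 0.155-0.164. Power rises because the conditional log odds ratio moves away from zero, from about 0.44 to 0.47-0.61. The SE narrows only on the standardized percentage scale (step 5).

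The association may be modest. Section 6.6 gives no reason for choosing the factor, so its prognostic strength is not documented. Exclusion 17 removes candidates whose screening UDS are all positive, which truncates the contrast and makes the largest assumed gaps less plausible.

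Finally, Table 1 justifies exclusion 17 by expected non-completion, so baseline UDS may well pass the attrition screen. That is a fair point, but entry is then likely rather than fixed. For the secondary UDS models, section 11.3.2 gives no full covariate list, so extending the term to them is a matter of consistency and not a documented omission.

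**Conclusion.** The point holds for the overall (time-averaged) treatment effect. One of the two randomization factors is absent from a primary model that the protocol writes out in full, and only a data-driven screen could bring it in. If the stratum is prognostic, the model-based SE is too wide for the true sampling variation, the test is conservative, and some power is forgone relative to an adjusted analysis.

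The size cannot be derived from the protocol. It is negligible at an assumed stratum odds ratio of 3 and material only if the association is strong (6 to 12). These figures assume ten weekly outcomes, complete data, no site effect and correlation 0.65. It is a worthwhile improvement in efficiency and prespecification, and no threat to the planned power or to control of false positives.

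The check also exposes an inconsistency: the hypothesis and sample size concern the overall percentage, whereas section 11.3.1 points to the treatment-by-week interaction.

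**What to change.** - Add the baseline stimulant-UDS stratum (yes/no) as a prespecified fixed effect in the primary model, and in the stimulant-free and drug-free UDS models, whatever the attrition screen shows.
- Report the standardized (marginal) difference in percent stimulant-free alongside the odds ratio, because the conditional odds ratio changes meaning when the stratum is added.
- Reconcile section 11.3.1 with sections 11.1.1 and 11.4 on whether the overall treatment effect or the treatment-by-week interaction is the primary test. If it is the overall effect, state the contrast that averages over weeks: in the code as written, week is not a class variable, so the treatment coefficient alone refers to week zero.

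The cost is one model term, using a variable already held for randomization, plus a small post-estimation step for the standardized difference and a clarifying sentence in the protocol. No new data are needed and the sample size does not change.

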11.0 ANALYTICAL PLAN

11.1 Statistical Hypotheses

11.1.1 Primary Hypothesis

The primary hypothesis is that a significantly greater percentage of TAU+SCT, relative to TAU, participants will be stimulant-free during the weeks of the active treatment phase (see section 6.5.1).

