The model formulation implies the same treatment effect in each site. The effect of the intervention on change in response from baseline will be addressed by the treatment by week interaction parameter. Due to the possibility that CTPs may differ in their success at helping participants become/remain stimulant-free, each regression model will adjust for site effects. Site will be included in the GLMM model as a random effect based on the participation of 12 CTPs. Assumptions of linearity will be examined by adding a restricted cubic spline to represent nonlinearity (Harrell, 2001). Assumptions for the covariance structure that provides the best fit to the data will be analyzed using the COVTEST statement under SAS Proc GLIMMIX. Since GLMM inference is only valid if data are missing at random (MAR), logistic regression analyses will be conducted to identify patterns of attrition and to determine if there is differential attrition by treatment condition. A binary indicator variable for missing data will be regressed on treatment assignment and other covariates. Variables that are associated with attrition at or below the α =0.10 level of significance will be included in subsequent analyses where the assumption of data missing at random (conditional on covariates) is required (Verbeke and Molenberghs, 2000).

If the random effects model unexpectedly fails to converge, then a general estimating equation (GEE) approach will be employed treating site as a fixed effect. If this model is utilized, then missing data (see Table 6) will be imputed using standard multiple imputation procedures, since GEE inference is only valid if data are missing completely at random (MCAR). SAS Proc MI will be used to create five complete data sets

using multiple imputation. Each data set subsequently be analyzed using SAS Proc GENMOD (the GEE procedure), and the results combined using SAS Proc MIANALYZE.

Urine Drug Screen - Stimulant result		Time Line Follow Back (TLFB)				
Result	Result	At least one positive day	All days negative	Some days negative, some missing	All days missing	
-	-	+	-	-	-	
+	-	+	+	+	+	
+	+	+	+	+	+	
+	0	+	+	+	+	
0	0	+	Missing	Missing	Missing	
_	0	+	-	-	-	

Table 6:	Stimulant-	use assignment	t for study	week as a	a function	of TLFB and	UDS result
			•				

Note: '0'=missing, '+'=positive and '-'=negative

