For a number of the remaining secondary outcomes, the effect of TAU+SCT, relative to TAU, is considered for both the active phase and follow-up phase. For these outcomes, a reference is made to controlling for baseline values. In the context of these analyses, the 'baseline value' for the active phase is the value of the outcome prior to randomization. If the analyses reveal a significant treatment effect during the active phase, then the 'baseline value' for the follow-up phase will be the outcome prior to randomization; this analysis will evaluate whether the effect observed during the active treatment phase is maintained through follow-up. If the analyses reveal no significant treatment effect during the active phase, then the 'baseline value' for the outcome measured at the end of the active phase; this analysis will evaluate whether a treatment effect becomes evident over a longer period of time (i.e., a "sleeper" effect).

5. The ASI- Lite

The seven areas of functioning measured by the ASI- Lite (medical status, employment status, drug use, alcohol use, family status, legal status, psychiatric status) will be assessed at baseline, the end of the active treatment phase and at the 3- and 6-month follow-up visits. These data will be analyzed using a repeated measures mixed model with group, time, time X group interaction and baseline values controlled as noted above. Significance of Group is declared if the joint effect of the Group and Group X time interaction (as defined by a change in log-likelihood) was significant (p<0.05). These 7 tests will be performed without adjustment for multiple testing.

6. Sexual Risky Behavior as assessed by the RAB

The sex risk scale of the RAB, which produces a score ranging from 0-28, will be assessed at baseline, the end of the active treatment phase and at the 3- and 6-month follow-up visits. The sex risk score data will be analyzed using a repeated measures mixed model with group, time, time X group interaction and baseline values controlled as noted above. Significance of Group is declared if the joint effect of the Group and Group X time interaction (as defined by a change in log-likelihood) is significant (p<0.05).

7. Cocaine/METH craving as assessed by the BSCS

The BSCS craving score, which ranges from 0-12, is assessed weekly during the active treatment phase and at the 3- and 6-month follow-up visits. These data will be analyzed using a repeated measures mixed model.

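### The only parameter named for the primary effect is the treatment-by-week slope, but the hypothesis and the sample size concern a difference in level

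*Protocol*

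**What the plan says.** Section 11.1.1 hypothesises that "a significantly greater percentage of TAU+SCT, relative to TAU, participants will be stimulant-free during the weeks of the active treatment phase", and section 11.3.1 repeats this. It is a statement about how many participants are stimulant-free, not about how fast that share changes.

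Section 11.4 sizes the trial on one probability per arm, 0.6 under TAU, and says that "this study will detect a group difference if the probability of stimulant-free urines in the TAU+SCT group is at least 0.7". The correlation is compound symmetric at 0.65, and neither probability has a time trend. The result is 528 participants, 264 per arm, for 80% power at two-sided 0.05.

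Section 11.3.1 codes the model as "model Y = treatment week treatment*week / dist=binary link=logit covb solution". The class statement reads "class site treatment", so week is continuous. The text agrees: "Assumptions of linearity will be examined by adding a restricted cubic spline to represent nonlinearity". The only sentence that ties the intervention effect to a parameter is "The effect of the intervention on change in response from baseline will be addressed by the treatment by week interaction parameter", and section 11.3.2 repeats it for the secondary repeated-measures models.

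For the ASI-Lite and the RAB sex risk scale, section 11.3.2 gives an explicit decision rule: "Significance of Group is declared if the joint effect of the Group and Group X time interaction" is significant. The primary outcome has no such rule.

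**The concern.** A slope and a level are different quantities. An arm that is ten points better in every week has a large level difference and no slope difference. An arm whose advantage shrinks over time is better throughout, yet has a negative interaction. The synopsis asks whether smoking-cessation treatment improves, worsens or does not affect stimulant use, so the sign of the tested parameter matters.

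The reference to change from baseline does not bridge the gap. The response is weekly status during active treatment. Baseline urine status stratifies the randomisation (6.6), but in the stated model it is neither a response nor a covariate.

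At stake are whether the stated 80% power belongs to the test that is run, and whether two analysts following section 11.3.1 would reach the same primary conclusion. The interim check in 11.6 looks at control-arm rates and correlations, so it cannot repair a mismatch of this kind.

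**Working it through.** **Inputs.** From 11.4: TAU 0.6, TAU+SCT 0.7, correlation ρ = 0.65 (compound symmetry), 264 per arm, two-sided 0.05, 80% power. From 7.4: a ten-week active phase. Assumed: T = 10 weekly outcomes (11.4 does not state the number used), no missing weeks, no site effect.

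**The plan's own figure.** For a level difference at a single time point:

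- Pooled formula: [1.96·√(2·0.65·0.35) + 0.8416·√(0.24 + 0.21)]² / 0.10² = 356 per arm, or 376 with continuity correction.
- Factor for averaging T correlated weeks: (1 + (T − 1)ρ)/T = (1 + 9·0.65)/10 = 0.685.
- 376 × 0.685 = 258 per arm, or 516 in total, 2.3% below 528. Without the continuity correction: 356 × 0.685 = 244 per arm, 488 in total.
- T = 7 with the correction gives exactly 264 per arm.

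So 528 is of the size that a time-averaged level difference needs. Constant 0.6 versus 0.7 gives no finite sample size for a slope.

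**Planning scenario, 0.70 versus 0.60 in every week.**

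- Averaged contrast: SE = √[(0.24 + 0.21)·0.685/264] = 0.0342; z = 0.10/0.0342 = 2.93; power = Φ(2.93 − 1.96) = 83%. The information matrix for the coded logit terms gives 82.7%, and a 300-replicate GEE simulation 82%.
- Interaction: the true slope difference is exactly zero, so power is 5% at any sample size (5% in the simulation).
- Treatment coefficient, if week is coded 1 to 10: this is the difference at week 0, with 76% power. It is not the average over weeks 1 to 10.
- Joint 2-df test of treatment and interaction: 74%.

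**Linear fade, 0.72 in week 1 to 0.66 in week 10, against 0.60.**

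- The average difference is 0.69 − 0.60 = 0.09 and the SE 0.0343, so z = 2.62 and power is about 75% (74% from the logit model).
- The slope difference is −0.06/9 = −0.00667 per week. With Σ(week − 5.5)² = 82.5, its SE = √[(0.24 + 0.214)·0.35/82.5/264] = 0.0027. Then z = −2.47, and the interaction is significant and negative in about 69% of trials. Simulations of per-participant slopes gave 60% and 63%, and the logit model 74%.

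**Benefit only from week 4, 0.70 versus 0.60.**

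- The average difference is 7 × 0.10/10 = 0.07 with SE about 0.0345. Power is about 54% across methods.
- The slope difference is 0.10 × 10.5/82.5 = 0.0127 per week, where 10.5 is the sum of (week − 5.5) over weeks 4 to 10. Divided by 0.0027, z is about 4.7 and power exceeds 99% (97% by simulation).

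| TAU+SCT against TAU at 0.60 | Averaged contrast | Interaction |
|---|---|---|
| Constant 0.70 | 83% | 5% |
| Fading 0.72 to 0.66 | about 74% | 60–74%, negative sign |
| 0.70 from week 4 only | about 54% | 97% or more |
| Equal in week 1, 0.70 by week 10 (linear logit) | 32% | about 99% |
| 0.49 rising to 0.70, average logit difference zero | 5% | over 99% |

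**The case against.** Three points can be made for the plan.

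First, section 11.3.1 does not say that the primary decision rests on the interaction. It assigns that parameter to change from baseline. Where the authors fix a decisive parameter they do so expressly, as for the ASI-Lite, the RAB and cigarettes per day. The model also contains a treatment term and prints the coefficients and their covariance, so any linear contrast can be formed. This stands. A reader might infer that the model cannot test the hypothesis, or that a steady benefit would necessarily be reported as null. The document supports neither. It supports saying that the one parameter named is the wrong one and that no decisive contrast is designated.

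Second, the week-0 reading of the treatment coefficient depends on coding week as 1 to 10, which the protocol does not state. Centred at 5.5, the same coefficient would be the mid-period difference. This also stands, so the point is conditional.

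Third, a delayed effect is plausible here. The quit date falls at the end of week 3, the inhaler and contingency management belong to the post-quit phase, and 11.6 expects only an indirect effect on stimulant use. The slope is much sharper for that pattern. This is a real trade-off, but a diverging effect is not what 11.1.1 hypothesises or 11.4 sizes.

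The general allowance in 11.3 for adjusting analyses covers constraints in the data, not the choice of what is tested. Nor is this detail left to an SAP, because the protocol itself names a parameter that conflicts with its hypothesis.

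**Conclusion.** The mismatch is real and should be corrected before analysis. Under the protocol's own planning values, the named parameter has 5% power where the matching contrast has about 83%, so the stated 80% does not belong to it. With a benefit in every week that fades, the interaction points towards harm in roughly 60 to 74% of trials, depending on the method.

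Confidence in the mismatch is high because it rests on the text. The power figures are illustrative. They assume ten weekly outcomes, 264 per arm, correlation 0.65, no missing weeks and no site effect, and they approximate the planned mixed model rather than reproduce it. What would be concluded in practice is less certain, because the correct contrast is available from the same fit and an analyst might choose it.

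**What to change.** State in 11.3.1 that the primary test is the treatment contrast averaged over weeks 1 to 10. Either drop the interaction from the primary model, or keep it and obtain the contrast with an ESTIMATE or LSMEANS statement at the mean week, (1 + 10)/2 = 5.5. State how week is coded. Report the result as a difference in percentage stimulant-free with a 95% confidence interval. Make the treatment-by-week interaction a secondary description of timing, remove the claim that it measures change from baseline, and align the general sentence in 11.3.2.

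The cost is wording and one statement of code, with no new data. The downside should be stated openly: an effect that begins only after the quit date is detected less often, about 54% against 97% or more for the slope if benefit starts in week 4. The joint 2-df test already used for the ASI-Lite and RAB can be reported as supportive for that pattern.

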11.3 Analysis Plan

Each primary and secondary efficacy outcome measure will be analyzed for the intent-to-treat (ITT) population. While there is every intention to be complete in describing the analyses to be performed, it is not possible to anticipate every contingency, and some adjustments may be required to meet constraints posed by the structure of the data. Constraints such as non-linearity, non-normality, etc. may lead to different but more appropriate approaches to analysis.

All statistical tests will be conducted at the 5% Type I error rate (two-sided). When multiple tests are conducted, the chance of finding a significant difference in one of the tests, when in fact no difference exists, is greater than the stated Type I error rate. The investigators are aware of the multiple testing issues and will interpret results with caution and use confidence intervals where possible.

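### The fallback GEE for the primary outcome fixes only five imputations, which leaves avoidable Monte Carlo error in a borderline p-value

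*Protocol*

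**What the plan says.** The primary analysis in section 11.3.1 is a generalized linear mixed model (GLMM) of weekly stimulant-free status. Under missing at random it uses the observed weeks and imputes nothing, as section 11.3.4 confirms.

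Imputation enters through the fallback: "If the random effects model unexpectedly fails to converge, then a general estimating equation (GEE) approach will be employed", with site as a fixed effect. Then "SAS Proc MI will be used to create five complete data sets", each is analysed with Proc GENMOD, and "the results combined using SAS Proc MIANALYZE". Section 11.3.4 repeats the fallback without the number.

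Section 11.3.1 also says that the effect of the intervention on change from baseline is "addressed by the treatment by week interaction parameter". Section 11.3.2 (items 1 and 2) carries the primary endpoint's imputation methods over to the 3- and 6-month urine screen models and to drug-free weeks. The protocol gives no reason for five, no expected share of missing weeks and no check of Monte Carlo error.

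**The concern.** Each run of a multiple imputation draws different random values, so the pooled estimate and its p-value vary with the seed. The variation shrinks as imputations are added and grows with the information lost to missing data. With five imputations it can be large enough to matter when the result lies near the two-sided 5% threshold. If the GLMM fails to converge, this analysis becomes the primary one. A borderline primary conclusion could then differ between two runs of the same program on the same data. A pre-specified fallback should remove that kind of arbitrariness, and here nearly all of it can be removed by changing one number.

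**Working it through.** **Inputs from the protocol.** Five imputations, pooled by Rubin's rules, with treatment by week as the named term (11.3.1). Two-sided 5% tests (11.3). 264 per arm, stimulant-free probabilities 0.6 and 0.7, and "a maximum correlation between any 2 time points of 0.65" under compound symmetry (11.4). Ten weekly outcomes (7.4).

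**Assumed.** The amount of missing data. Dropout was varied from 10 to 50% and FMI from 0.05 to 0.5.

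**The plan's own figure.** The number five has no derivation to reproduce. The sample size was re-derived only to check the simulation setting. With ten measurements the repeated-measures factor is (1 + 9 × 0.65)/10 = 0.685. The continuity-corrected two-proportion size of 376 per arm gives 376 × 0.685 = 257.6, rounded up to 258 per arm or 516 in total. That is within 3% of the stated 528. Without the continuity correction the total is 484 to 492. Nothing below depends on this difference.

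**Formulas.** Let B be the between-imputation variance and T the total variance with unlimited imputations, so FMI ≈ B/T. With m imputations the pooled estimate carries extra variance B/m. Hence:

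- SD of z between seeds ≈ √(FMI/m)
- relative efficiency ≈ 1/(1 + FMI/m)
- standard error inflation ≈ √(1 + FMI/m)

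**FMI in a trial-like setting.** The simulation used 264 per arm, ten weeks, correlation 0.65, monotone logistic imputation and GEE. For treatment by week the mean FMI was 0.07, 0.15, 0.23 and 0.38 at 10, 20, 30 and 50% dropout. For the time-averaged treatment effect it was 0.01 to 0.05.

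| Term | FMI | Seed SD of z, m = 5 | Seed SD of z, m = 50 |
|---|---|---|---|
| Treatment by week, 10% dropout | 0.07 | √(0.07/5) = 0.12 | 0.04 |
| Treatment by week, 50% dropout | 0.38 | √(0.38/5) = 0.28 | 0.09 |
| Time-averaged, low | 0.01 | √(0.01/5) = 0.04 | 0.01 |
| Time-averaged, high | 0.05 | √(0.05/5) = 0.10 | 0.03 |

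One seed SD either side of z = 1.96 gives p of 0.038 to 0.066 at FMI 0.07 and 0.025 to 0.092 at FMI 0.38 (m = 5).

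**Precision.** At m = 5, FMI 0.2 gives efficiency 1/1.04 = 0.96 and a standard error larger by √1.04 = 1.020. FMI 0.4 gives 1/1.08 = 0.93 and √1.08 = 1.039. At m = 50 efficiency is at least 0.99 for both.

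**P-values under Rubin's rules with t degrees of freedom (200,000 draws).**

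| FMI | m | Central 95% of p when unlimited-m p = 0.05 | Chance of p > 0.05 when unlimited-m p = 0.03 |
|---|---|---|---|
| 0.05 | 5 | 0.031–0.083 | 4% |
| 0.1 | 5 | 0.024–0.107 | 14% |
| 0.2 | 5 | 0.016–0.155 | 29% |
| 0.3 | 5 | 0.011–0.202 | 38% |
| 0.5 | 5 | 0.005–0.287 | 49% |
| 0.3 | 20 | 0.024–0.101 | 12.5% |
| 0.3 | 50 | 0.032–0.078 | 2.3% |
| 0.3 | 100 | 0.036–0.069 | 0.2% |

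**Single simulated data sets, 30% dropout, 80 seeds.** For treatment by week with near-unlimited p = 0.069, m = 5 gave p from 0.014 to 0.225 and m = 50 gave 0.049 to 0.079. For the time-averaged effect with near-unlimited p = 0.030, m = 5 gave 0.021 to 0.051.

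**The case against.** Four objections have weight.

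**The analysis is contingent.** The five data sets are used for the primary outcome only if the GLMM fails to converge, which the protocol itself calls unexpected. Harm also needs a borderline result and appreciable missing information. This stands, and it keeps the point minor.

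**Five is not an error.** A reader might infer that five imputations make the fallback test invalid or inflate its type I error. The document does not support that. Pooling with Proc MIANALYZE includes the 1 + 1/m variance term and the t reference distribution, which allow for the small number. What remains is poor reproducibility and a small loss of precision.

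**The missing share is unknown.** Table 6 makes a week missing only when both urine samples are absent and no use is reported, which limits the share. The 15 to 19% completion that section 4.2.1 quotes comes from a different cocaine trial and describes completion, not missing weeks here. An FMI of 0.2 to 0.4 corresponds to roughly 30 to 50% dropout for the interaction and should not be taken as expected. This stands, so the low end is shown too.

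**The tested term matters.** The primary hypothesis and the sample size (0.6 against 0.7) read naturally as an overall difference. For a time-averaged effect the seed matters little. This also stands. The larger figures apply to the treatment-by-week term that section 11.3.1 names.

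It can also be said that 50 is not derived from a stated tolerance and that 20 already gives 0.985 efficiency at FMI 0.3. For efficiency that is enough. For reproducibility it is less so: 20 still leaves a 12.5% chance that an unlimited-m p of 0.03 is reported above 0.05, against 2.3% with 50.

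**Conclusion.** The point holds as a minor, nearly costless improvement. If the GLMM does not converge, five imputations leave a seed SD of z of about 0.12 to 0.28 for the treatment-by-week term, assuming 10 to 50% dropout, and a borderline result can change sides of 0.05 on the seed alone. With 50 the SD is about 0.04 to 0.09. For a time-averaged effect the SD with five is only about 0.04 to 0.10. The standard error penalty is about 2 to 4% at an assumed FMI of 0.2 to 0.4. All these sizes rest on assumed missingness, because the protocol states none.

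Two wider inferences are not supported. The planned primary result does not depend on a seed, because the GLMM imputes nothing. Nor is the absence of a stated seed a defect: that is a programming or SAP matter, and the SAP is not at hand. A fixed seed would make the result repeatable but would leave the Monte Carlo error in place.

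**What to change.** In section 11.3.1, replace five with at least 50 imputations. Because section 11.3.2 reuses the primary endpoint's imputation methods, the same edit covers the 3- and 6-month urine screen models and the drug-free-week model wherever imputation is used. The cost is one number in the protocol and the program, and negligible computing time. Sample size, trial conduct and participants are unaffected.
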